#### **4. Objectives**

#### **Statement of Hypotheses and Specific Aims:**

In the VHA health care system, Parkinson's disease (PD) presents a high illness burden as a result of compromised mobility and quality of life (QOL). Pharmacological agents and surgical options that alleviate impairments do not fully address needs of those with PD. Motor rehabilitation is effective and lacks the side effects of pharmacology and surgery, but the underlying neural basis for motor improvements is largely unknown. To design better treatments for patients with PD that will improve motor function and QOL, we seek to understand the relationship between improved motor function and neural changes. Over the last 5 years, the PI has tested the efficacy of PD-adapted tango, which improved mobility and QOL in adults with PD after training. Adapted tango is a novel, patient-friendly method of motor rehabilitation in which participants learn to alternate leading (internally guided: IG) and following (externally guided: EG) partnered movement. IG and EG motor tasks are likely mediated by striato-thalamo-cortical (STC) and cerebello-thalamo-cortical (CTC) circuitry, respectively in healthy controls. Because PD causes dysfunction in the basal ganglia, patients have difficulty with IG tasks. However, this impairment can be remediated by motor rehabilitation that uses skills similar to those used when "leading" in tango, in which participants engage cognitively in planning and selecting movements. Conversely, abundant evidence shows that external cues, such as those used for "following" during tango, facilitate movement in PD, presumably because EG tasks access CTC circuitry and bypass the basal ganglia. During "following", participants with PD can exploit multiple external cues, which may aid rehabilitative effects. **In individuals with PD, we aim to improve our understanding of lower limb motor control and the circuitry involved (Aim 1), determine the relative effectiveness of targeted IG and EG training, and explore neural mechanisms of mobility improvement through adapted tango (Aim 2).** To accomplish this goal,

first we will use fMRI to investigate neural correlates of lower limb control with a foot-tapping task under IG and EG conditions in veterans with and without PD (Aim 1). Imaging studies have previously employed foot-tapping, which is used clinically to assess lower limb control. To achieve Aim 2, we will 1) evaluate the relative effectiveness of practicing IG movement (leading) versus practicing EG movement (following) versus a behavioral control (health education) for improved mobility and lower limb control, and 2) assess neural activity changes underlying improvements in lower limb control across training groups. The long-term goal is to optimize motor rehabilitative interventions for veterans with PD and understand the neural mechanisms through which the training is effective in order to further improve rehabilitation strategies for this and similar diseases.

**Specific Aim 1: Determine neural correlates of internally guided and externally guided foot-tapping in individuals with and without PD.**

**Hypothesis 1:** In healthy controls, IG and EG foot-tapping are related to task-specific neural networks of the striato-thalamo-cortical and cerebello-thalamo-cortical circuits, respectively. In those with PD relative to controls, IG foot-tapping will result in increased activation of both the STC (posterosuperior putamen, ventral anterolateral thalamus, rostral supplementary motor area, primary motor cortex) and the CTC (cerebellum (Larsell lobules IV, V, and VI), ventral posterolateral thalamus, primary somatosensory cortex, ventral premotor cortex) circuits. EG foot-tapping will result in increased activation in the CTC circuit only.

**Specific Aim 2: Determine the effect, in individuals with PD, of internally guided versus externally guided training compared to a behavioral control on: 1) mobility, and 2) whether improved mobility and foot-tapping performance after training correlate with changes in activation and resting-state functional connectivity patterns in IG and EG foot-tapping networks.**

**Hypothesis 1:** If mobility gains are related to training in planning and selecting movements, then those in IG will demonstrate greater improvements than those in EG or control. If mobility gains are related to exploiting cues during training, then those in EG will demonstrate greater improvements than those in IG or control.

**Hypothesis 2:** If improved IG foot-tapping performance and mobility (as determined in Aim 2, Hypothesis 1) are related to IG training and planning movement, then we will see IG training-related increased activation in the STC circuit and decreased activation in CTC circuitry. If improved EG foot-tapping performance and mobility are related to EG training and attending to cues, then we will see corresponding increased activation in the CTC circuit.

**Hypothesis 3:** Resting-state functional connectivity patterns will reflect training effects, with connectivity increases primarily in the STC circuit following IG training and in the CTC circuit after EG training; minimal changes will occur following the control intervention.

## **5. Study design and Methods**

**Overview:** To accomplish Aim 1, we will use functional Magnetic Resonance Imaging (fMRI) to determine neural circuitry underlying IG and EG foot-tapping in 24 veterans with and 24 veterans without idiopathic, mild-moderate PD (Hoehn & Yahr stages II-III). To accomplish Aim 2, we propose a randomized controlled trial to evaluate the relative effectiveness of IG and EG movement to improve mobility in veterans with PD. We will also measure corresponding changes in neural activation during IG and EG foot-tapping, as a result of intervention. Participants will be randomized

to receive EG, IG or behavioral control (BC; health education) training over 12 weeks. Participants will be tested on all outcome measures while “OFF” and “ON” medications at a standardized time of day. We are observing participants in outcome measures while OFF medications in order to avoid dyskinesia, and medication fluctuations that may impact functional activity of networks of interest. Participants will complete outcome measure testing for mobility, QOL, executive function, procedural learning, spatial cognition, and foot-tapping 1 week before training (pre), and 1 week (post) and one month (follow-up) after completing all training. Using fMRI we will also investigate the relationship of changes in neural activation in the participants before and immediately after training.

### **Measures that will be used in screening and outcome assessments:**

#### **Descriptors**

**Health Screening:** Participants will be screened for general health with the Project Health Questionnaire at the first testing session.

**Vision:** Measurement of visual acuity will be performed with Early Treatment for Diabetic Retinopathy Study acuity chart (ETDRS) at 3 m. Visual impairment will be determined as none (better than Snellen acuity 20/30), mild (between 20/30 and 20/60), moderate (20/60 and 20/200) or severe (greater than 20/200) in the best eye (World Health Organization ICD-10, 2006).

**Hearing:** All participants will be asked if they use a hearing aid, and if yes, the frequency with which they use it. Pure tone audiometry, using a GSI-61 Clinical Audiometer, will assess hearing sensitivity in an acoustically controlled environment (available at the Atlanta Rehab R&D CoE). Participants will be excluded if pure-tone threshold average sensitivity at 0.5, 1.0, and 2.0 kHz exceeds 40 dB.

**Disease Severity:** Participants with PD will be evaluated for disease severity at each evaluation with the Movement Disorder Society Unified Parkinson Disease Rating Scale (motor subscale III: UPDRS, Movement Disorder Society 2003) by a qualified and experienced rater blinded to study purposes

**Mental Status:** Participants will be assessed for mental status with the Montreal Cognitive Assessment (MoCA; Nasreddine et al., 2005).

**Handedness and Leggedness Inventory:** Participants will self-report their handedness with the Edinburgh Handedness Inventory to help baseline their movements for analysis. This inventory will indicate whether the participant is dominantly right- or left-handed (Edinburgh Handedness Inventory: Oldfield, R.C., 1971). We will also use the Survey of Handedness and Leggedness (Schneiders, 2010)

**Outcome Measures:** Participants will undergo a comprehensive battery of motor, cognitive and psychosocial measures to evaluate the efficacy of the intervention. See table 2 for a summary of these measures, which are described in more detail below.

**Calendar of Adverse Events:** Participants will be given calendars and asked to keep track of ‘adverse events’, including falls and near misses. They will be asked about adverse events once per month, and at each evaluation. Their responses will be recorded.

#### **Motor:**

- **Six minute walk test** (6MWT; Guyatt et al., 1985). 6MWT is a valid and reliable measure of overall mobility and physical functioning in older people (Lord&Menz, 2002).
- **Single and Dual Timed Up and Go test** (TUG), (Morris S et al., 2001) - A measure of functional mobility, the TUG (Shumway Cook et al., 2000) has demonstrated validity and reliability. The participant is timed while they rise from a chair, walk 3 m as quickly as possible, turn around and return to the chair. Dual-task ability will be measured with the TUG cognitive (TUGc) and manual conditions (TUGm). In TUGc the participant counts backwards by 3s from a random number between 20 and 100. In TUGm the participant carries a full glass of water. Time  $\geq 15$  s for TUG-c and time  $\geq 14.5$  s for TUGm indicates impaired dual-task ability and increased fall risk. The PI noted improvements on this measure after adapted tango training within older adults with visual impairment, and in those with PD during piloted data collection completed in October 2011.
- **Four square step test**- clinical test of dynamic standing balance (Dite & Temple 2002). It involves stepping over low objects (2.5cm) and movement in 4 directions. The Four square step test has high sensitivity, specificity and predictive value for identifying differences between groups in a population of older adults.
- **30 second Chair Stand test**: Lower body strength is associated with the ability to perform lifestyle tasks such as climbing stairs, getting in and out of a vehicle or bath, and will be measured with the 30-s chair stand (chair stand) test 15, in which the participant rises from a chair to full standing as many times as possible in 30 seconds.

### **Postural control & Fall Risk:**

- **Berg Balance scale** (BBS; Berg et al., 1995). BBS is a performance-oriented measure of fall risk and balance in older adults, consisting of 14 items rated from 0 to 4. Aim 2 is powered with a predicted 4-point improvement in the BBS because this measure was improved repeatedly to clinical significance in previous studies. The BBS has excellent inter- and intra-rater reliability (0.98-0.99) and a maximum score of 56 possible points
- **Dynamic gait index** (DGI; Shumway-Cook & Woollacott, 1995). 8 items, including walking while changing speed and turning the head, walking over and around obstacles, and stair climbing. DGI scoring is based on a 4-point scale from 0 to 3: 0 indicates severe impairment and a score of 3 indicates normal ability. A total score  $< 20/24$  indicates risk for falling. The DGI has been shown to have inter-rater reliability of .96, test-retest reliability of .96.
- **Fullerton Advanced Balance scale** (Hernandez D, and Rose DJ, 2008). The FAB Scale includes items intended to better identify older adults who may be experiencing increased fall risk as a result of sensory system impairments.
- **Limits of Stability test and other tests of the Neurocom Equitest system** – Evaluated with Neurocom Equitest systems, this computerized posturography test evaluates stability limits in 8 directions with measures of maximum excursion and directional control. Adapted tango training will require participants to move their center of mass beyond their stability limits when stepping; therefore, we expect increased stability limits as a result of training.
- **Gait**- Spatiotemporal parameters of habitual (i.e., preferred, comfortable), backward and fast-as-possible walking will be assessed by a 6 m computerized GAITRite walkway (CIR Systems, Inc. Havertown, PA, USA). Variables of interest include velocity, stride length, and stride variability, which have been improved previously through adapted tango training.

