Treatment of PD Mobility Impairment: Pharmacology and surgery do not fully address the needs of those with PD. Effective motor rehabilitation is necessary, and should be safe, participant-friendly, promote high adherence and have demonstrated efficacy in improving disease severity, mobility and QOL. Traditional exercise programs often suffer from high attrition rates because of high patient task demand and lack of social interaction. Ideally, exercise activities should engage and sustain interest, because 60% of all Americans older than 65 do not achieve recommended daily amounts of physical activity. Activity levels in individuals with PD are even further reduced.

Several mobility programs are effective (e.g., movement strategies, dance, tandem biking, tai chi) for people with PD. Better mechanistic understanding of beneficial exercise effects could improve the design of targeted motor rehabilitation interventions for particular symptoms (e.g., freezing, bradykinesia, and various disease stages of PD). This information would be of great clinical significance to veterans and others with motor impairment of all etiologies, as well as due to PD.

In the last five years, the PI has published a series of studies of training in adapted Argentine-tango (adapted tango) dance showing gains in mobility and balance, maintained one month later in individuals with PD (Hoehn & Yahr stages II-IV). Participant-friendly, adapted tango had low attrition (15%) demonstrating patient acceptance and feasibility with a diverse patient population. In classes, participants alternated between two motor training approaches: a) leading, consisting of internally guiding (IG) movement plans, and b) following, consisting of responding to external guidance (EG). While feasibility and promising outcomes have been demonstrated, previous studies were not designed to make inferences about the causal mechanisms of this intervention. Of interest now is what leading and following, in isolation, contribute to the observed benefits, because evidence shows IG and EG tasks activate distinct neural pathways, which may impact training effects.

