**Hypothesis 1:** Power calculations for Aim 2 are based upon an assumed 4-point improvement and effect sizes  $> 0.8$  on the BBS after 12 weeks of adapted tango, which was attained previously (see Preliminary Studies), and the minimal detectable change on the BBS in parkinsonism is 2.84 points. Therefore, with a total sample size of 63 participants (21 participants in each of 3 groups: IG, EG, and BC) a repeated measures (RM) ANOVA with 3 levels of repeat will be sensitive to between-within interaction main effect size of  $f(v) = 0.44$  ( $F_{4,114} = 2.45$ ) with a power of 0.80 at  $\alpha=.05$ . Post hoc sensitivity to effects between groups will be  $d = 0.90$ , and within groups,  $d_z = 0.65$ . To reflect an anticipated 20% attrition, we will recruit an additional 4 participants per group. Thus we will recruit 25 participants per group, for a total of 75 individuals with PD recruited for Aim 2. **Hypothesis 2:** 25 participants per group will be sufficient to detect effects for the imaging (activation and resting state) components of Aim 2 as well, based on studies conducted to determine reasonable sample sizes for fMRI studies, that demonstrate at least 20 participants in each group are necessary. **Hypothesis 3:** Differences in RSfc have been noted between different groups of individuals with PD in sample sizes of 16 per group; therefore, with 25 individuals per group, we will be able to detect differences between groups.

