## Statistical Analysis Plan for Aim 2, Hypothesis 1, 2 and 3:

- **Participant demographics:** Descriptive statistics will characterize groups. One-way ANOVA will determine differences, if any, between groups on baseline measures.
- **Behavioral Outcome measures:** A 3 group (IG, EG, BC) x 3 time (pre, post test, follow-up (1-month later)) RM ANOVA will be used to detect main effects. Appropriate post hoc tests will be used to determine within- and between-group differences,  $p<0.05$ , for **BBS, the primary outcome** measure upon which Aim 2 is powered. Statistical tests run on all secondary variables will be corrected for multiple comparisons.
- **Brain Activation Analyses for Aim 2, Hypothesis 2:** Similar to Aim 1 procedures, average percent signal change for IG and EG tasks (relative to baseline) for each participant will be extracted from the centers of gravity of the activated regions and submitted to hierarchical regression analyses to determine whether they correlate with behavioral measures (foot-tapping absolute timing errors and average amplitude). Disease severity and PD duration will be covariates. To determine the effects of time and training status we will submit the percent signal change to a 3 group (IG, EG and BC) X 2 time (pre, post) RM ANOVA. Post-hoc analyses will be corrected for multiple comparisons. The **primary outcome** will be t-contrast maps and effect size maps from ANOVA, which will be evaluated for changes in STC and CTC circuits.

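### The primary Berg Balance Scale stops at 56 and the analysis has no ceiling handling; if baseline scores are high, the IG-versus-EG contrast is biased toward zero, by an amount the documents cannot fix

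*Combined protocol and SAP*

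**What the plan says.** All references are to the combined protocol and SAP.

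- **Scale.** Section 5 (Postural control & Fall Risk) describes the BBS as 14 items scored 0 to 4, with "a maximum score of 56 possible points".
- **Planning gain.** The same section says "Aim 2 is powered with a predicted 4-point improvement in the BBS". Section 7 (Power Analyses for Aim 2, Hypothesis 1) says "Power calculations for Aim 2 are based upon an assumed 4-point improvement and effect sizes" above 0.8, states that this was attained before, and adds that "the minimal detectable change on the BBS in parkinsonism is 2.84 points".
- **Entry.** Section 5 (Screening) requires Hoehn & Yahr stage II-III. Section 6 (Table 4) sets a minimum walking ability plus sensory, cognitive, depression and MRI criteria. Nothing limits baseline BBS.
- **Analysis.** Section 7 (Statistical Analysis Plan for Aim 2) names BBS as primary and plans a 3 group x 3 time repeated-measures ANOVA. It continues: "Appropriate post hoc tests will be used to determine within- and between-group differences". There is no baseline-adjusted or ceiling-aware model and no report of scores at the maximum.
- **Interpretation.** Section 5 (Potential Pitfalls/Alternative Approaches, item 1) says what follows if IG and EG do not differ on outcome measures while results match the earlier combined training: patients and providers will be told they may choose either type.

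**The concern.** With a maximum of 56, a 4-point gain needs a starting score of 56 - 4 = 52 or lower. Someone starting at 54 or above can gain at most 2 points, less than the 2.84-point minimal detectable change that the plan cites. If both tango arms improve, the better arm meets the cap more often and loses more of its gain. An analysis that reads 56 as a true score then underestimates the difference between the arms.

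This bears on the trial's own question, since Aim 2, Hypothesis 1 asks whether IG beats EG or the reverse. That contrast compares two active arms, and it is the one most exposed when both move toward the top of the scale. A null result caused by the cap could be taken as evidence that the two forms of training are equivalent.

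**Working it through.** **1. The plan's own power figure.** Inputs from Section 7: 63 participants, three groups, three visits, f(V) = 0.44, alpha 0.05. Using a noncentral F with 4 and 2 x (63 - 3) = 120 degrees of freedom and noncentrality 0.44² x 63 = 12.2, power is 0.792. The stated 0.80 is therefore reproduced. (The printed 114 degrees of freedom correspond to 60 participants; this does not affect the point here.) The calculation contains no ceiling. It is for the omnibus interaction and assumes no IG-versus-EG difference in points.

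**2. Assumptions needed because the documents are silent.**
- SD 5, from 4 / 0.8. The plan says effect sizes above 0.8, so on this reading the SD is at most 5.
- Pre-post correlation 0.7.
- 20 per arm, from 25 recruited less 20% attrition.
- Baseline mean 42 to 52.
- True gains of 2 in one tango arm and 6 in the other, a 4-point difference centred on the planned 4.

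**3. Power without a cap.** SD of change = 5 x √(2 x (1 - 0.7)) = 3.87. Standardised difference = 4 / 3.87 = 1.03. Noncentrality = 1.03 x √(20/2) = 3.27 on 38 degrees of freedom. Two-sided power at 0.05 is about 0.89.

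**4. Shrinkage of the difference.** For a latent mean m, the expected loss to the cap is 5 x [φ(z) - z(1 - Φ(z))] with z = (56 - m)/5. The loss at baseline is the same in both arms and cancels. Example at baseline mean 48:
- Gain 2: m = 50, z = 1.2, loss 5 x 0.0561 = 0.28.
- Gain 6: m = 54, z = 0.4, loss 5 x 0.2304 = 1.15.
- Observed difference = 4 - (1.15 - 0.28) = 3.13.

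The share starting above 52 (whole-point scores) is 1 - Φ((52.5 - mean)/5). Power is from simulation with scores rounded and capped at 56.

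| Baseline mean | Start above 52 | Observed difference (true 4) | Shrinkage | Change-score power (0.89 uncapped) |
|---|---|---|---|---|
| 42 | 1.8% | 3.9 | 3% | 0.87 |
| 44 | 4.5% | 3.8 | 6% | 0.86 |
| 46 | 9.7% | 3.5 | 12% | 0.82 |
| 48 | 18.4% | 3.1 | 22% | 0.75 |
| 50 | 30.9% | 2.6 | 35% | 0.63 |
| 52 | 46.0% | 2.0 | 50% | 0.46 |

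**5. Sensitivity to the assumptions.** Take gains of 6 and 1.5. Their difference of 4.5 points is the plan's post hoc d = 0.90 at SD 5. With correlation 0.5 and 21 per arm, power falls from 0.81 to 0.80 / 0.79 / 0.75 / 0.69 / 0.59 / 0.46 at the same six means. At SD 4, same gains and correlation, it falls from about 0.94 to 0.94 / 0.94 / 0.93 / 0.89 / 0.79 / 0.61. For the omnibus 3 x 3 interaction with gains 4, 4 and 0 (SD 5, correlation 0.5), it falls from about 0.78 to 0.77 / 0.77 / 0.76 / 0.73 / 0.68 / 0.60. The direction is the same in every scenario; only the size changes.

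**6. What each part of a remedy does.** Under the step 2 assumptions, adjusting for baseline BBS without censoring gives power of about 0.91 / 0.88 / 0.84 / 0.74 at means 46 / 48 / 50 / 52. Most of the lost power therefore comes back from baseline adjustment. The estimate still shrinks as in step 4, because randomised arms have equal expected baselines. Treating 56 as right-censored removes that shrinkage. In a harsher scenario (gains 4 and 8), the censored model recovered about 3.9 to 4.0 points. Its power was 0.91 / 0.87 / 0.80 / 0.71, against 0.91 / 0.83 / 0.76 / 0.62 for the same model without censoring.

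**The case against.** - **The 4 points were reportedly seen on this same capped scale.** A gain observed on a 56-point scale already includes any ceiling loss in those samples. A reader might infer that the cap makes the planning assumption unattainable or the power statement wrong. The documents do not support that. It would require this population to start higher than the earlier ones, and the only hint is that the earlier gains are described for stages II-IV while this trial takes II-III. No stage mix is given, and one of the reports cited there is a single case study in severe disease. This objection stands.
- **Baseline BBS may be low enough for the cap not to matter.** This also stands: at means of 42 to 44 the loss is small. Testing OFF medication may add headroom. However, outcomes are measured both ON and OFF, and the plan does not say which BBS is primary, so that protection is not secured.
- **A dramatic loss needs dramatic gains.** With gains of 4 and 8, change-score power falls to about 0.25 at a mean of 52. A reader might quote that as the size of the problem. It doubles the planned gain in one arm and has no source in the documents.
- **A capped BBS alone does not trigger the patient-choice advice.** Item 1 under Potential Pitfalls speaks of outcome measures in the plural and also requires results to match the earlier training. Six-minute walk, Timed Up and Go, Limits of Stability and gait are secondary motor measures that do not share this cap. A reader might infer that a null BBS leads straight to the advice; the text is narrower than that.
- **The censored model is favoured by its test.** The data were simulated from the normal latent scores that the model assumes, whereas BBS is a sum of 14 ordinal items. This stands, and it is why the model should be a companion analysis.

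**Conclusion.** The point holds in conditional form. The cap at 56, the absence of a baseline BBS limit and the absence of ceiling handling are all plain in the documents. With similar baselines, the cap pulls the IG-versus-EG contrast toward zero.

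The size depends on a baseline mean and SD that the documents do not give. Under the assumptions in step 2, shrinkage runs from about 3% at a mean of 42 to 50% at 52, and power from 0.87 down to 0.46. It is minor at 42 to 44 and material from about 48 upward.

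The documents do not show that scores will in fact be near the cap, that the trial will miss a real difference, or that the repeated-measures ANOVA must be replaced. Nor do they show that the Fullerton Advanced Balance scale, already a secondary measure, has more headroom, so it cannot be presented as the answer.

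**What to change.** 1. **Section 7, Statistical Analysis Plan for Aim 2.** Keep the repeated-measures ANOVA. Pre-specify a companion between-group BBS analysis with baseline BBS as a covariate and 56 treated as right-censored.
2. **Same section.** Report the share of participants scoring 56, and the share above 52, by arm and visit.
3. **Section 5, Potential Pitfalls/Alternative Approaches, item 1.** State that a null BBS contrast will not count toward a finding of no difference between IG and EG if the ceiling-aware analysis disagrees or many scores are at 56. Set in advance what share counts as many. Leave in place the existing conditions about several outcome measures and agreement with the earlier training.

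The cost is SAP wording and one extra model on data already collected, with no new visits, measures or participants. The downside is reliance on a normal latent score, which is acceptable in a companion analysis. If few scores reach 56, the censoring will change little.
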